### **7.1.1. Packaging and Labeling**

LY3074828 will be supplied by the sponsor or its designee in accordance with current GMP, and labeled according to the country's regulatory requirements. The following products will be supplied by Lilly:

- pre-assembled investigational LY3074828 PFSs, 1-mL and 2-mL
- LY3074828 (solution for injection) SFS

Each SFS will be supplied as a 1- or 2-mL single-use syringe designed to deliver LY3074828 125 mg/mL. Members of Lilly Delivery and Device Research and Development will attend the study site and assemble the SFS and appropriate device components, to form the investigational AIs.

Each investigational device will be individually identified and labeled according to US regulatory requirements for investigational devices.

## **7.2. Method of Treatment Assignment**

Subjects will be randomized within 1 study part (Part A or Part B) to 1 of 2 dosing regimen arms ([Table AMAQ.2](#) and [Table AMAQ.3](#)). In addition, the sequence of injections on Days 1 and 2 (fast/slow versus slow/fast) for subjects participating in Part B will be randomized.

Randomization will be performed using a computer-generated randomization schedule.

### **7.2.1. Selection and Timing of Doses**

The actual time of all dose administrations will be recorded in the subject's eCRF.

## **7.3. Blinding**

This is an open-label study; however, subjects in Part B will not be informed as to whether the AI is fast or slow injection speed.

## **7.4. Dose Modification**

Dose adjustments are not permitted in this study.

## **7.5. Preparation/Handling/Storage/Accountability**

The IPs for this study will be:

- LY3074828 in an investigational PFS
- LY3074828 in an SFS incorporated into an investigational AI

Investigational product will be stored refrigerated at 2°C to 8°C (36°F to 46°F) in its original carton to protect from light. Investigational product should not be frozen or shaken. Sites will be required to monitor temperature of the on-site storage conditions of the IP. The investigator or designee must confirm appropriate temperature conditions have been maintained, as communicated by the sponsor, during transit for all IP received and ensure any discrepancies are reported and resolved before use of the study treatment.

The SFs assembled into AIs containing LY3074828 and the PFSs containing LY3074828 should be allowed to warm to room temperature for at least 30 minutes before use.

Parts to be used for the assembly of AIs may be stored at room temperature.

Only participants enrolled in the study may receive IP or study materials, and only authorized site staff may supply IP. All IP should be stored in an environmentally-controlled and monitored (manual or automated) area in accordance with the labeled storage conditions with access limited to the investigator and authorized site staff.

The investigator is responsible for study treatment accountability, reconciliation, and record maintenance (such as receipt, reconciliation, and final disposition records).

## **7.6. Treatment Compliance**

The IP will be administered at the clinical site, and documentation of treatment administration will occur at the site.

## **7.7. Concomitant Therapy**

Over-the-counter or prescription medications, including herbal medication, are not permitted within 14 days prior to dosing and throughout the study. However, stable doses of oral contraceptive or hormone-replacement therapy are permitted at the discretion of the investigator.

Paracetamol/acetaminophen (up to 2 g/day) is permitted at the discretion of the investigator. Additional drugs are to be avoided during the study, unless required to treat an AE.

If the need for concomitant medication arises, inclusion or continuation of the subject may be at the discretion of the investigator after consultation with a Lilly clinical pharmacologist (CP) or clinical research physician (CRP). Any additional medication used during the course of the study must be documented.

## **7.8. Treatment after the End of the Study**

This section is not applicable for this study.

## 8. Discontinuation Criteria

### 8.1. Discontinuation from Study Treatment

Randomized subjects who discontinue the study prematurely for any reason should complete the early discontinuation (ED) procedures performed as shown in the Schedule of Activities (Section 2). The reason for, and the date of discontinuation, will be collected for all subjects.

#### 8.1.1. Discontinuation of Inadvertently Enrolled Subjects

If the sponsor or investigator identifies a subject who did not meet enrollment criteria and was inadvertently enrolled, a discussion must occur between the Lilly CP or CRP and the investigator to determine if the subject may continue in the study. If a subject is inadvertently enrolled into Part B and this is discovered prior to the scheduled administration of the second dose, the second dose would not be administered. Any subjects that are inadvertently enrolled subjects will be followed for safety.

### 8.2. Discontinuation from the Study

Subjects will be discontinued in the following circumstances:

- Enrollment in any other clinical study involving an IP or enrollment in any other type of medical research judged not to be scientifically or medically compatible with this study
- Participation in the study needs to be stopped for medical, safety, regulatory, or other reasons consistent with applicable laws, regulations, and good clinical practice
- The investigator decides that the subject should be discontinued from the study
- The subject requests to be withdrawn from the study

Subjects who discontinue the study early will have ED procedures performed as shown in the Schedule of Activities (Section 2).

### 8.3. Subjects Lost to Follow-up

A subject will be considered lost to follow-up if he or she repeatedly fails to return for scheduled visits and is unable to be contacted by the study site. Site personnel are expected to make diligent attempts to contact subjects who fail to return for a scheduled visit or were otherwise unable to be followed up by the site.

## 9. Study Assessments and Procedures

Section 2 lists the Schedule of Activities, detailing the study procedures and their timing (including tolerance limits for timing).

[Appendix 2](#) lists the clinical laboratory tests that will be performed for this study.

[Appendix 5](#) provides a summary of the maximum number and volume of invasive samples, for all sampling, during the study.

The specifications in this protocol for the timings of safety and sample collection are given as targets to be achieved within reasonable limits. Modifications may be made to the time points based upon emerging clinical information. The scheduled time points may be subject to minor alterations; however, the actual time must be correctly recorded in the eCRF. Late collection outside the stipulated time allowances or failure to obtain samples due to clinical issues, such as problems with equipment, venous access, or subject defaulting on a scheduled procedure, will not be considered as protocol deviations but the site will still be required to notify the sponsor in writing via a file-note.

Unless otherwise stated in subsections below, all samples collected for specified laboratory tests will be destroyed within 60 days of receipt of confirmed test results. Certain samples may be retained for a longer period, if necessary, to comply with applicable laws, regulations, or laboratory certification standards.

Investigators must document their review of each laboratory safety report.

### 9.1. Efficacy Assessments

This section is not applicable for this study.

### 9.2. Adverse Events

Investigators are responsible for monitoring the safety of subjects who have entered this study and for alerting Lilly or its designee to any event that seems unusual, even if this event may be considered an unanticipated benefit to the subject.

The investigator is responsible for the appropriate medical care of subjects during the study.

Investigators must document their review of each laboratory safety report.

The investigator remains responsible for following, through an appropriate health care option, AEs that are serious or otherwise medically important, considered related to the IP or the study, or that caused the subject to discontinue the IP before completing the study. The subject should be followed until the event resolves, stabilizes with appropriate diagnostic evaluation, or is reasonably explained. The frequency of follow-up evaluations of the AE is left to the discretion of the investigator.

After the informed consent form is signed, study site personnel will record, via eCRF, the occurrence and nature of each subject's preexisting conditions. Additionally, site personnel will record any change in the condition(s) and the occurrence and nature of any AEs.

The investigator will interpret and document whether or not an AE has a reasonable possibility of being related to study treatment, study device, or a study procedure, taking into account concomitant treatment or pathologies.

A "reasonable possibility" means that there is a cause and effect relationship between the IP, study device, and/or study procedure and the AE.

Planned surgeries should not be reported as AEs unless the underlying medical condition has worsened during the course of the study.

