### **9.2.1. Serious Adverse Events**

An SAE is any AE from this study that results in one of the following:

- death
- initial or prolonged inpatient hospitalization
- a life-threatening experience (that is, immediate risk of dying)
- persistent or significant disability/incapacity
- congenital anomaly/birth defect
- important medical events that may not be immediately life-threatening or result in death or hospitalization but may jeopardize the subject or may require intervention to prevent one of the other outcomes listed in the definition above
- when a condition related to the investigational device (PFS or AI) necessitates medical or surgical intervention to preclude either permanent impairment of a body function or permanent damage to a body structure, the serious outcome of "required intervention" will be assigned

Study site personnel must alert the Lilly CRP/CP, or its designee, of any SAE as soon as practically possible.

Additionally, study site personnel must alert Lilly Global Patient Safety, or its designee, of any SAE within 24 hours of investigator awareness of the event via a sponsor-approved method. If alerts are issued via telephone, they are to be immediately followed with official notification on study-specific SAE forms. This 24-hour notification requirement refers to the initial SAE information and all follow-up SAE information.

Although all AEs are recorded in the eCRF after signing informed consent, SAE reporting to the sponsor begins after the subject has signed informed consent and has received IP. However, if an SAE occurs after signing informed consent, but prior to receiving IP AND is considered reasonably possibly related to a study procedure then it MUST be reported.

Investigators are not obligated to actively seek AEs or SAEs in subjects once they have discontinued from and/or completed the study (the subject summary eCRF has been completed). However, if the investigator learns of any SAE, including a death, at any time after a subject has been discharged from the study, and he/she considers the event reasonably possibly related to the study treatment or study participation, the investigator must promptly notify Lilly.

Pregnancy (maternal or paternal exposure to IP) does not meet the definition of an AE. However, to fulfill regulatory requirements any pregnancy should be reported following the SAE process to collect data on the outcome for both mother and fetus.

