#### **9.2.1.3. Suspected Unexpected Serious Adverse Reactions**

Suspected unexpected serious adverse reactions (SUSARs) are serious events that are not listed in the IB and that the investigator identifies as related to IP or procedure. Lilly has procedures that will be followed for the recording and expedited reporting of SUSARs that are consistent with global regulations and the associated detailed guidances.

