### **10.3.1. Safety Analyses**

#### **10.3.1.1. Clinical Evaluation of Safety**

All IP and protocol procedure AEs and PCs will be listed, and if the frequency of events allows, safety data will be summarized using descriptive methodology.

The incidence of symptoms for each treatment will be presented by severity and by association with IP as perceived by the investigator. Symptoms reported to occur prior to study entry will be distinguished from those reported as new or increased in severity during the study. Each symptom will be classified by the most suitable term from the medical regulatory dictionary.

The number of IP- and device-related SAEs and any related PCs will be reported.

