## **9.4 Safety and Tolerability Assessments**

### **9.4.1 Adverse events**

Where changes in severity are recorded in the Case Report Form (CRF), each separate severity of the AE will be reported in the listings, only the most severe will be used in the summary tables. A pre-existing condition is defined as an AE that starts before the subject has provided written informed consent and is ongoing at consent. A non-treatment emergent AE is defined as an AE which starts after informed consent but prior to dosing. A treatment-emergent AE is defined as an AE which occurs postdose or which is present prior to dosing and becomes more severe postdose.

All AEs will be listed. Treatment-emergent AEs will be summarized by treatment, severity and relationship to the study drug. The frequency (the number of AEs, the number of subjects experiencing an AE and the percentage of subjects experiencing an AE) of treatment-emergent AEs will be summarized by treatment, Medical Dictionary for Regulatory Activities (MedDRA) version 20.1 system organ class and preferred term. The summary and frequency AE tables will be presented for all causalities and those considered related to the study drug. Any serious AEs will be tabulated.

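### Protocol 9.2 defines a reasonable possibility of relatedness as an existing causal link, so plausible but unconfirmed events may be coded not related

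*Protocol*

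**What the plan says.** Protocol 9.2 tells the investigator to document "whether or not an AE has a reasonable possibility of being related to study treatment, study device, or a study procedure", taking concomitant treatment and pathologies into account. The sentence after it defines the key term: a reasonable possibility "means that there is a cause and effect relationship between the IP, study device, and/or study procedure and the AE". No other section defines a threshold for relatedness.

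The investigator's relatedness call is then used in several places:

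- SAP 9.4.1: "The summary and frequency AE tables will be presented for all causalities and those considered related to the study drug".
- Protocol 10.3.1.1: symptom incidence is presented "by severity and by association with IP as perceived by the investigator", and the number of drug- and device-related SAEs is reported.
- Protocol 9.2.1.3: SUSARs are "serious events that are not listed in the IB and that the investigator identifies as related to IP or procedure".
- Protocol 9.2.1: an SAE learned of after discharge is notified if "he/she considers the event reasonably possibly related to the study treatment or study participation, the investigator must promptly notify Lilly". An SAE after consent but before dosing must be reported if it meets the same possibility wording for a study procedure.
- Protocol 9.2: being considered related to the product or the study is one of the triggers for following an AE until it resolves, stabilizes or is explained.

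**The concern.** The question asks about possibility, while its definition requires that the causal link exists. An investigator who follows the question and one who follows the definition could code the same event differently. The second would code as not related an event that drug, device or procedure may plausibly have caused but that nobody can confirm.

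That kind of event is to be expected here. The study is open-label with no placebo arm and 18 subjects randomized per arm, so causality will seldom be affirmed for a single event. Safety and tolerability are primary objectives in both parts. The programme also cites relatedness as safety evidence. Protocol 3.2 reports no drug-related treatment-emergent AEs of Grade 2 or higher in Study AMAA, and none considered related to study drug in Study AMAD. A related-event count from this study would probably be read in the same way.

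**Working it through.** The documents give no related-event rate or count to reproduce, so the check is of the text.

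**1. Term against definition.** The question in Protocol 9.2 turns on *a reasonable possibility of being related*. The definition turns on *there is* a cause and effect relationship, with no *may* or *could*. The two sentences set different thresholds.

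**2. Whether wording elsewhere supplies the softer threshold.**

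- Protocol 9.2.1 uses *reasonably possibly related*. This is the adverbial form of the one relatedness phrase the protocol defines, so it naturally takes the 9.2 definition with it.
- Protocol 9.2.1.1 uses *believed to be related* for device events, and Protocol 10.3.1.1 uses *as perceived by the investigator*. These say whose judgement counts, not what threshold applies.
- Protocol 9.2.1.3 and SAP 9.4.1 use *related* without qualification.

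None of these overrides the definition.

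**3. What depends on the relatedness call.**

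- *Related-event tables and related-SAE counts (SAP 9.4.1; Protocol 10.3.1.1).* Direct dependence.
- *SUSAR definition (Protocol 9.2.1.3).* It depends on the investigator's call. The sentence names no separate sponsor judgement of causality, although sponsor procedures for recording and expedited reporting are mentioned.
- *Pre-dose and post-discharge SAEs (Protocol 9.2.1).* Reporting is conditional on relatedness, so the rule that every SAE is reported does not act as a backstop.
- *Follow-up of AEs (Protocol 9.2).* The triggers are alternatives: serious or otherwise medically important, related, or leading to discontinuation of the product. Only an AE that meets none of the others could lose follow-up through its coding.

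**4. What does not depend on it.**

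- The endpoint is incidence of treatment-emergent AEs, defined without regard to causality (Protocol Table AMAQ.1 and Appendix 1; SAP 9.4.1).
- SAP 9.4.1 states "All AEs will be listed", and its tables are also produced for all causalities.
- After dosing and while the subject is on study, "study site personnel must alert Lilly Global Patient Safety, or its designee, of any SAE within 24 hours of investigator awareness of the event". This carries no relatedness condition.
- Infections, injection-site reactions and hypersensitivity reactions are of special interest, with details collected whenever they are reported (Protocol 9.2.1.2). Injection-site findings are also assessed on schedule and summarized (Protocol 10.3.1.2.3; SAP 9.4.7).

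**5. Size.** The number of events that would change category depends on how investigators apply the sentence, and the documents do not give it. What can be stated is the resolution of the table. If all 18 subjects randomized to an arm are dosed, recoding one subject's only related event moves that related incidence by 1/18 = 5.6 percentage points.

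**The case against.** The best defence is that the defining sentence names the kind of relationship meant, causal rather than merely temporal, and does not demand certainty. Appendix 1 draws that distinction when it says that an AE is temporally associated with a product and need not be caused by it. The operative instruction still asks about possibility. On this view the sentence is loose drafting that a trained investigator would read sensibly. That reading is available and may well be what was intended, but the sentence does not say it, and the contradiction with the defined term remains.

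The second defence is containment, and most of it stands. The endpoint, the listings, the all-causality tables and the reporting of on-study SAEs after dosing are protected. The sponsor monitors safety data throughout (Protocol 9.4.5), and the reactions of most interest are captured whatever their causality. This limits the consequence, but it does not protect the related-event tables, the SUSAR definition as written, or SAE reporting before dosing and after discharge.

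A reader might infer something stronger: that possible but unproven reactions are in fact coded unrelated and drop out of the related tables and SUSAR screening. The documents do not support that. No section directs such coding or requires proof, and the result follows only if investigators apply the definition literally. Nor can the argument rest on a first use of new devices. The documents call the devices investigational, but Protocol 3.1 says the 1-mL syringe was used in Study AMAE, and Protocol 3.3 refers to a device brochure with known and expected risks for the autoinjector.

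**Conclusion.** Wrong as written. The only threshold that the protocol defines for relatedness contradicts the term it defines. The consequence is a risk of under-attribution and inconsistent coding, conditional on literal application. It is not an established bias.

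The exposure is confined to the related-event tables, the related-SAE counts, SUSAR identification, pre-dose and post-discharge SAE reporting, and follow-up of AEs that meet no other trigger. A reader might want to attach a percentage to the shortfall, but the documents give neither the number of plausibly related events nor the share that could be confirmed, so any figure would be assumption alone. The same definition applies in every arm, and nothing in the documents suggests a differential effect on the syringe or injection-speed comparisons.

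**What to change.** In the defining sentence of Protocol 9.2, change *there is* to *there may be* a cause and effect relationship, and leave the rest of the sentence as it stands. Use that standard wherever relatedness is applied: SAE reporting (9.2.1), adverse device effects (9.2.1.1), SUSARs (9.2.1.3), the safety summaries (10.3.1.1) and the related-event tables (SAP 9.4.1). Put the same wording in the eCRF guidance, so that the coding instruction matches the protocol.

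The cost is a wording change and a site note. Design, sample size and analysis methods are untouched. The downside is that related-AE counts may be slightly higher.

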### **9.2.1. Serious Adverse Events**

An SAE is any AE from this study that results in one of the following:

- death
- initial or prolonged inpatient hospitalization
- a life-threatening experience (that is, immediate risk of dying)
- persistent or significant disability/incapacity
- congenital anomaly/birth defect
- important medical events that may not be immediately life-threatening or result in death or hospitalization but may jeopardize the subject or may require intervention to prevent one of the other outcomes listed in the definition above
- when a condition related to the investigational device (PFS or AI) necessitates medical or surgical intervention to preclude either permanent impairment of a body function or permanent damage to a body structure, the serious outcome of "required intervention" will be assigned

Study site personnel must alert the Lilly CRP/CP, or its designee, of any SAE as soon as practically possible.

Additionally, study site personnel must alert Lilly Global Patient Safety, or its designee, of any SAE within 24 hours of investigator awareness of the event via a sponsor-approved method. If alerts are issued via telephone, they are to be immediately followed with official notification on study-specific SAE forms. This 24-hour notification requirement refers to the initial SAE information and all follow-up SAE information.

Although all AEs are recorded in the eCRF after signing informed consent, SAE reporting to the sponsor begins after the subject has signed informed consent and has received IP. However, if an SAE occurs after signing informed consent, but prior to receiving IP AND is considered reasonably possibly related to a study procedure then it MUST be reported.

Investigators are not obligated to actively seek AEs or SAEs in subjects once they have discontinued from and/or completed the study (the subject summary eCRF has been completed). However, if the investigator learns of any SAE, including a death, at any time after a subject has been discharged from the study, and he/she considers the event reasonably possibly related to the study treatment or study participation, the investigator must promptly notify Lilly.

Pregnancy (maternal or paternal exposure to IP) does not meet the definition of an AE. However, to fulfill regulatory requirements any pregnancy should be reported following the SAE process to collect data on the outcome for both mother and fetus.

